9.1.2.2.2 Unexpected Adverse Reactions

Unexpected Adverse Reaction Definition

An unexpected adverse reaction is any untoward and unintended response that is related to the administration of the study agent, at any dose that is not consistent with the applicable product information (eg, current version of the Investigator's Brochure for an unauthorized investigational medicinal product or summary of product characteristics for an authorized product).

All suspected unexpected serious adverse reactions (SUSARs) will be the subject of expedited reporting. The sponsor and/or the appointed representative(s) shall ensure that all relevant information about a SUSAR that is fatal or life-threatening is reported to the relevant competent authorities and IEC/IRB within 7 days after knowledge by the sponsor of such a case and that relevant follow-up information is communicated within an additional 8 days. All other SUSARs will be reported to the relevant competent authorities and IEC/IRB within 15 days after knowledge by the sponsor of such a case. All investigators should follow up SUSARs until the event is resolved or until, in the opinion of the investigator, the event is stabilized or determined to be chronic. Poststudy SUSARs that occur after the subject has completed the clinical study must be reported by the investigator to the sponsor.

Warnings and Precautions

Hypersensitivity Reactions: Do not administer NH002 to subjects with known or suspected hypersensitivity to perflutren.

Serious Cardiopulmonary Reactions: Serious cardiopulmonary reactions including fatalities have occurred uncommonly during or shortly following perflutren-containing microsphere administration, typically within 30 minutes of administration. The risk for these reactions may be increased among subjects with unstable cardiopulmonary conditions (acute myocardial infarction, acute coronary artery syndromes, worsening or unstable congestive heart failure, or serious ventricular arrhythmias). Always have cardiopulmonary resuscitation personnel and equipment readily available before NH002 administration and monitor all subjects for acute reactions.

Systemic Embolization: Subjects with known right-to-left, bidirectional, or transient right-to-left cardiac shunt(s) are **excluded** from this study, but it is important to note the following. When administering study agent to subjects with a cardiac shunt, the microspheres can bypass filtering by the lung and enter the arterial circulation. Subjects with shunts should be assessed for embolic phenomena following study agent administration. The study agent is only for IV administration; do not administer by intra-arterial injection(s).

Ventricular Arrhythmia Related to High Mechanical Index: High ultrasound MI values may cause microsphere cavitation or rupture and lead to ventricular arrhythmias. Additionally, end-systolic triggering with high MIs has been reported to cause ventricular arrhythmias. Study agent is not recommended for use at MIs greater than 0.8.

9.1.2.2.3 Clinical Laboratory Evaluation

The hematology and clinical chemistry laboratory analyses will be performed at local laboratories. Reference ranges will be supplied by the local laboratories and used by the investigator to assess the laboratory data for clinical significance and pathological changes.

Methods (including whether samples are taken fed or fasting) and timing for assessing, recording and analyzing each laboratory variable should follow local guidelines, within the confines of the protocol timeframes. The following laboratory safety tests will be performed at screening and treatment visits:

Hematology

Hgb, HCT, WBC count (total and differential), red blood cell count, PLT, mean cell volume, mean cell hemoglobin (MCH), and MCH concentration

Clinical Chemistry

Creatinine, BUN, AST, ALT, ALP, total bilirubin, albumin, total protein, sodium, potassium, chloride, glucose, bicarbonate, calcium, magnesium, and phosphorus

9.1.2.2.4 Other Laboratory Variables

Screening for pregnancy will be performed (serum or urine β -HCG at screening and serum and urine β -HCG before dosing on Day 1, for WoCBP only).

Other laboratory variables collected are:

- Coagulation studies of TT and aPTT
- Cardiac troponin I

9.1.2.2.5 Vital Signs

Vital signs (BP, body temperature, RR, and HR) will be recorded at screening, before injection, during injection and imaging (beginning approximately 5 minutes prior to and continuing until 10 minutes after injection), and 30, 60, and 120 minutes post-injection, in a standardized manner.

9.1.2.2.6 Pulse oximetry

SpO₂ will be assessed pre-injection, during injection and imaging (beginning approximately 5 minutes prior to and continuing until 10 minutes after), and at 30, 60, and 120 minutes post-injection.

9.1.2.2.7 Physical Examination

At screening, a complete physical examination will be performed. A focused physical examination will be performed before dosing and during dosing at the following time points for each contrast injection: 30, 60, and 120 minutes post-injection. Any changes will be recorded and assessed. Each PE assessment will be scored as either normal or abnormal.

9.1.2.2.8 Electrocardiogram

Standard 12-lead ECGs will be performed at screening, before dosing on Day 1, and at 10, 30, and 60 minutes post-injection. Safety assessments will be based on the results of the standard 12-lead ECGs. The following parameters will be evaluated: First degree heart block (HB), second degree HB, complete HB, atrial arrhythmia, junctional rhythms, ventricular arrhythmia, LVH (left ventricular hypertrophy), other chamber enlargement, Q-wave infarct, ST-T wave changes; ischemia suspected, nonspecific ST-T wave changes, QTc interval prolongation. Each 12-lead ECG assessment will be scored as either normal or abnormal.

In addition, modified 12-lead ECG monitoring will be performed during imaging to prevent the ECG electrodes from affecting the accessibility of the optimal imaging windows of echocardiography. Imaging can be performed with a modified 12-lead ECG, by repositioning the V5-V6 leads upward. If any clinically significant ECG changes indicative of arrhythmia or S-T segment change are identified within 10 minutes after dosing from the modified 12-lead ECG monitoring, an additional standard 12-lead ECG examination will be performed subsequently when the earliest ECG change occurs.

To further enhance the quality of the modified 12-lead ECGs:

1. The investigator should make best efforts to minimize the displacement of the electrodes for the modified 12-lead ECG compared with the standard 12-lead ECG.
2. The repositioning of the ECG leads for echocardiography should only involve the V5-V6 leads, which have been shown to have minimal effect on ECG waveform.²⁵
3. To describe the shifted leads, study personnel should make appropriate annotations in the study records/subject file.

Refer to [Image Evaluation Guidelines](#) for information on central review procedures.

9.1.3 Appropriateness of Measurements

The efficacy and safety assessments planned for this study are generally recognized as reliable, accurate, and relevant to the diagnostic modality and underlying disease/condition.

9.2 Dose Escalation Committee (DEC)

To enhance the safety and integrity of the study data, a DEC will evaluate clinical, laboratory, and electrocardiographic safety before advancing to the next dose level. It will consist of sponsor personnel, the independent medical monitor, and the investigator(s) at the study site.

A sentinel review approach will be followed whereby the first review will be conducted at the end of the safety follow-up observation period for the first subject treated in Cohort 1 to determine if subsequent subjects may be dosed in the cohort. In order to review all cumulative safety data for Cohort 1, the next review will be conducted at the end of the safety follow-up observation period for the last subject treated in Cohort 1. This sentinel review approach will continue to be followed for all successive cohorts (ie, Cohort 2 and Cohort 3), in order to review safety data and to provide a recommendation on study continuation, recommended dose, or early termination in case there is a concern regarding safety. This will be repeated until the highest dose level has been evaluated.

Further details regarding timelines and specific responsibilities of the DEC will be provided in a separate Charter.

10 STATISTICAL METHODS

The statistical planning and analysis of the trial will be performed by the biostatistics department of the sponsor or designated contract research organization.

10.1 Statistical and Analytical Plans

A statistical analysis plan will be prepared and finalized prior to database lock of the study. The statistical analysis plan will include full details of all planned statistical analyses and the dose selection strategy.

10.2 Datasets or Populations Analysed

Safety Set

The Safety Set (SS) will consist of all subjects receiving at least 1 injection of NH002.

Full Analysis Set

The Full Analysis Set (FAS) will consist of all enrolled subjects who have completed all study evaluation periods, and received 1 dose injection of NH002.

Per Protocol Set

The Per Protocol Set will be a subset of the Full Analysis Set and will include all subjects who completed all study evaluation periods, received 1 dose injection of NH002 and had no major protocol deviations. Further definition of the per protocol set will be specified in the statistical analysis plan.

10.3 Demographic and Other Baseline Characteristics

Demographic and baseline characteristic data will be summarized for each cohort and overall. Descriptive statistics (N, mean, standard deviation, median, minimum, and maximum) will be presented for continuous variables and the number and percentage of subjects in each category will be presented for categorical variables. No formal testing of demographic or baseline characteristics will be performed. The impact of any imbalances in demographics or baseline characteristic variables on treatment effect may be investigated in exploratory analyses on select efficacy or safety variables; such analyses will be documented in the statistical analysis plan, if applicable.

10.4 Safety Assessments

All safety assessments, including AEs, PEs, VS, ECGs, and clinical laboratory evaluations, where indicated, will be presented using descriptive statistics for each dose of NH002. Data will be summarized for each dose group and overall.

10.4.1 Safety Variables

- Adverse events recorded before injection, during injection and imaging, and post-injection;
- Any changes in PE findings
- Standard 12-lead ECGs assessed before injection and at 10, 30, and 60 minutes post-injection; an additional standard 12-lead ECG will also be conditionally performed at the earliest time point when any clinically significant ECG changes indicative of arrhythmia or S-T segment change are identified within 10 minutes after injection from the modified 12-lead ECG monitoring;
- Changes in VS assessed before injection, during injection and imaging (beginning approximately 5 minutes prior to and continuing until 10 minutes after), and at 30, 60, and 120 minutes post-injection;
- Changes in hematology and metabolic laboratory parameters taken before injection and 60, 120, and 240 minutes post-injection;
- SpO₂ assessed before injection, during injection and imaging (beginning approximately 5 minutes prior to and continuing until 10 minutes after), and at 30, 60, and 120 minutes post-injection.

10.5 Efficacy Variables

10.5.1 Definition of Primary Efficacy Endpoint

There are no primary efficacy endpoints for this study.

10.5.2 Definition of Secondary Efficacy Endpoints

- The percentage of subjects with moderate or complete LVO, defined by an LVO grade of 2 (moderate) or 3 (complete), as assessed by the blinded central reader(s);
- The percentage of subjects with complete LVO, defined by an LVO grade of 3 (complete), as assessed by the blinded central reader(s);
- The change from baseline on the LVEBD score, defined using a standard 12-segment model, as assessed by the blinded central reader(s). The LV endocardium of the 4- or 2-chamber apical views are divided into 6 segments, with 2 basal, mid-, and apical segments in each view. For each segment, LVEBD is graded as follows: 0 = inadequate border (border not visible); 1 = sufficient (border barely visible); 2 = good (border clearly visible). A total delineation score (0-24) is obtained by adding the scores from the 6 individual segments in each of the 2 views.
- The changes from baseline on LVEBD score of subjects with suboptimal LVEBD at baseline, as defined by 2 or more contiguous segments of 6 segments that cannot be visualized reliably in either the apical 4- and/or the 2-chamber view, as assessed by the blinded central reader(s);
- The duration of clinically useful contrast calculated by measuring the time between the disappearance of shadowing effect (useful effect starts) and the time when moderate or full LV enhancement and contrast enhancement are no longer adequate (useful effect ends), as assessed by the blinded central reader(s).

10.6 Methods of Analysis

The safety and efficacy variables of each dose of NH002 will be presented using descriptive statistics. A series of selection rules based on efficacy and safety will be applied to determine the maximum tolerated dose. If no single NH002 dose shows a clear benefit in safety or efficacy, the lowest dose of NH002 will be selected.

Secondary endpoints will be summarized by descriptive statistics. Graphical presentations of the data will be provided, where appropriate.

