High ultrasound mechanical index (MI) values may cause microsphere cavitation or rupture and lead to ventricular arrhythmias. Additionally, end-systolic triggering with high MIs has been reported to cause ventricular arrhythmias. The safety of NH002 at MIs greater than 0.8 will not be evaluated.

Number of Subjects:

Up to 36 subjects will be enrolled. If a subject is withdrawn from the study, except for those subjects who will be terminated early due to AEs, the subject may be replaced as necessary with another subject assigned to the same dose. Further subjects may be enrolled at a given dose level if additional data are necessary to establish safety and tolerability prior to dose escalation.

Treatment:

The contrast agent will be administered by IV bolus injection within 30 to 60 seconds, followed by a 10 mL saline flush over 10 seconds. The following dose regimens will be tested: 2.5 μ l/kg, 5.0 μ l/kg, 10.0 μ l/kg.

Subjects will be enrolled with sequential allocation to the NH002 doses. Each patient will undergo an unenhanced ultrasound examination and an NH002 contrast-enhanced examination on the same day at Day 1. Each subject will receive 1 of the following 3 NH002 doses: 2.5 μ l/kg, 5.0 μ l/kg, 10.0 μ l/kg IV bolus. Sequential allocation is as follows, if all 3 dose levels exhibit acceptable toxicity: the first 12 subjects will receive 2.5 μ l/kg, the next 12 will receive 5.0 μ l/kg, and the final 12 will receive 10.0 μ l/kg. (See [Section 7.5.1.2](#) for further details, including the definition of unacceptable toxicity for this trial.) The 12 subjects in each ascending cohort will be enrolled only if no serious adverse reactions or toxicity reactions have been observed within 7 days from completion of the safety observation period for the last subject in the preceding cohort.

A dose escalation committee (DEC) will evaluate clinical, laboratory, and electrocardiographic safety data before advancing to the next higher dose level. If stopping criteria for dosing as defined in [Section 7.5.1.2](#) is observed in a specific cohort, the previous dose level will be considered to be the maximum tolerated dose and no further increases in dose will be included in the study.

Duration of Treatment:

The duration of treatment is expected to last between 4 to 5 hours during 1 day, barring any unexpected adverse reactions.

Study Population:

To be eligible for study entry, subjects must satisfy all of the following inclusion criteria:

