To enhance the safety and integrity of the study data, a dose escalation committee (DEC) will evaluate clinical, laboratory, and electrocardiographic safety data, routinely before advancing to the next higher dose level/cohort. The DEC will consist of sponsor personnel, the independent medical monitor, and the investigator(s) at the study site. A sentinel review approach will be followed whereby the first review will be conducted at the end of the safety follow-up observation period for the first subject treated in Cohort 1 to determine if subsequent subjects may be dosed in the cohort. To review all cumulative safety data for Cohort 1, the next review will be conducted at the end of the safety follow-up observation period for the last subject treated in Cohort 1. This sentinel review approach will continue to be followed for all successive cohorts (ie, Cohort 2 and Cohort 3), to review safety data and to provide a recommendation on study continuation, recommended dose, or early termination in case there is a concern regarding safety. If treatment stopping criteria, as defined in [Section 7.5.1.2](#), is observed in a specific dosing

group, the previous dose will be considered to be the maximum tolerated dose and no further increases in dose will be included in the study.

Proceeding to the next higher dose level is permissible before completion of a cohort when no visible contrast effect and no safety concerns are observed in 4 subjects in a cohort. Such decision will be triggered by the sponsor in conjunction with the DEC, and as approved by the appropriate regulatory agencies.

A more conservative dose assignment, evaluation of an intermediate dose, and/or expansion of an existing dose level is permissible if such measures are needed for patient safety or for a better understanding of NH002 dose-related toxicity, and/or exposure. Such changes will be determined by the sponsor in conjunction with the DEC, and as approved by the appropriate regulatory agencies.

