2		
1. Remove Section 5.5.1 LVEBD Score for Subjects with Suboptimal LVEBD (LVEBD Score < 14 and at Least 4 Segments with a Delineation Rating of +1 or +2) at Baseline.2. Add Section 7.2.2 External Data Transfer.	
1. According to the protocol, the Suboptimal LVEBD at Baseline is as defined by 2 or more contiguous segments of 6 segments that cannot be visualized reliably in either the apical 4- and/or the 2-chamber view, as assessed by the blinded central reader(s).2. The external data is transferred by [REDACTED] Inc. and Trust Bio-sonics, Inc.

1. Introduction

This Statistical Analysis Plan (SAP) contains a more technical and detailed elaboration of the principal features of the analysis described in the protocol, and includes detailed procedures for executing the statistical analysis of the primary and secondary variables and other data. The SAP is finalized and signed prior to hard lock of the database.

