5.1. General Considerations

The safety and efficacy variables of each dose of NH002 will be presented using descriptive statistics. For continuous variables, the descriptive statistics (N, mean, standard deviation, median, minimum, and maximum) will be presented for safety variables, and the descriptive statistics (N, mean, standard deviation, median, minimum, maximum, and 95% CI) will be presented for efficacy variables. For categorical variables, the number and percentage of subjects in each category will be presented. Data will be summarized for each dose group and overall.

All data processing, summarization, and analyses will be performed using SAS Version 9.4.

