7.2. Appendix 2: Adds to Protocol-Planned Analyses

7.2.1. Re-screened Subjects

For re-screened subjects, information is taken from the last re-screening visit instead of the screening visit.

The number of subjects re-screened are summarized in Table 01.1: Summary of Subject's Disposition.

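### Protocol 10.6 lets efficacy help determine the maximum tolerated dose, which the synopsis and 7.1 define by toxicity alone, and the SAP holds no rule to settle it

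*Protocol*

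**What the plan says.** **Toxicity-only definition.** The Protocol synopsis (Treatment) says that if the dosing stopping criteria are met in a cohort, "the previous dose level will be considered to be the maximum tolerated dose". Protocol 7.1 repeats this: "the previous dose will be considered to be the maximum tolerated dose and no further increases in dose will be included in the study". The criteria are in Protocol 7.5.1.2. They are one SAE at least possibly related to the agent, or listed laboratory, cardiac or anaphylactic toxicity in 30% of subjects at a dose level. None of them concerns efficacy.

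**Efficacy-and-safety definition.** Protocol 10.6 says: "A series of selection rules based on efficacy and safety will be applied to determine the maximum tolerated dose". The next sentence is: "If no single NH002 dose shows a clear benefit in safety or efficacy, the lowest dose of NH002 will be selected". The rules are not listed.

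**Where the rules should be.** Protocol 10.1 says: "The statistical analysis plan will include full details of all planned statistical analyses and the dose selection strategy". SAP 5.1 repeats the opening sentence of 10.6 ("The safety and efficacy variables of each dose of NH002 will be presented using descriptive statistics") and leaves out the two dose-selection sentences. SAP Appendix 2, titled "Adds to Protocol-Planned Analyses", covers only re-screened subjects and external data transfer. The SAP does not mention an MTD.

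**A third output.** Protocol 9.2 and SAP 5.6 have the Dose Escalation Committee (DEC) give a recommended dose from safety data. Neither document relates it to the 10.6 choice.

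**The concern.** Whether a dose is tolerated is a safety question, and how well it opacifies the ventricle has no bearing on it. Protocol 10.6 gives one label to two things: the highest dose that patients tolerate, and the dose the sponsor would choose after weighing image quality against safety. All of these sections are current text, and nothing ranks one above another.

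What is at stake is the dose conclusion in the study report. A dose of 2.5 μl/kg chosen by default could be reported as the MTD when 5.0 or 10.0 μl/kg was tolerated. Safety and tolerability are the primary objective, and both documents call this a dose-finding study, so readers will look for that conclusion. Because the rule is unwritten, the endpoints and the threshold for a clear benefit could also be chosen after results are seen.

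**Working it through.** The plan states no power, error rate or operating characteristic, so there is no figure of its own to reproduce. The check applies both texts to every escalation outcome, then asks how often the conflicting outcome could arise.

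**Step 1. Both texts, outcome by outcome.** Doses are 2.5, 5.0 and 10.0 μl/kg. The last column assumes that the lowest-dose fallback applies and is read as the MTD.

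| First cohort to stop | MTD under synopsis and 7.1 | 10.6 fallback read as MTD |
|---|---|---|
| Cohort 1 | none named (no previous dose) | 2.5 |
| Cohort 2 | 2.5 | 2.5 |
| Cohort 3 | 5.0 | 2.5 |
| No cohort | none named | 2.5 |

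Only the cohort 3 row has two different numbers. In the cohort 1 row, a literal fallback selects the dose that has just met a stopping criterion.

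**Step 2. Chance that one cohort meets the 30% criterion.** Cohort size is 12 (Protocol 7.5.1.1). Since 0.30 × 12 = 3.6, the trigger is taken as 4 of 12. For a true toxicity rate p, q = P(X ≥ 4), with X binomial (12, p). The documents give no toxicity rates, so every p is an assumption. The single-SAE rule, early step-up, cohort expansion and replacement are left out.

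| p | 5% | 10% | 20% | 30% | 40% |
|---|---|---|---|---|---|
| q | 0.0022 | 0.0256 | 0.2054 | 0.5075 | 0.7747 |

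At p = 15%, q = 0.0922. At p = 2%, q = 0.0001.

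**Step 3. Cohort 3 stops, same rate at every dose.** The probability is q(1 − q)²:

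- 5%: 0.0022 × 0.9955 = 0.2%
- 10%: 0.0256 × 0.9494 = 2.4%
- 15%: 0.0922 × 0.8241 = 7.6%
- 20%: 0.2054 × 0.6313 = 13.0%

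**Step 4. Cohort 3 stops, rate rising with dose.** The probability is (1 − q₁)(1 − q₂)q₃:

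- 2/5/10%: 0.9999 × 0.9978 × 0.0256 = 2.6%
- 5/10/30%: 0.9978 × 0.9744 × 0.5075 = 49.3%
- 5/20/40%: 0.9978 × 0.7946 × 0.7747 = 61.4%

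In the same three cases no cohort stops with probability 97.2%, 47.9% and 17.9%.

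**Step 5. What these figures do not give.** They are the chance of a cohort 3 stop. Two different MTDs also require that the fallback applies and is read as the MTD. That further probability cannot be computed, because the 10.6 rule is not written in either document.

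**The case against.** **The fallback sentence says the lowest dose is selected, not that it is the MTD.** The drafter may well have meant a recommended dose, a term the protocol uses elsewhere. This stands as to likely intent, and it is why the consequence is conditional. But the sentence directly before it says the rules determine the MTD, so the text needs correcting whatever was meant.

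**Even when cohort 3 stops, it is arguable whether the fallback applies.** It requires that no dose shows a clear benefit in safety or efficacy, yet 10.0 μl/kg would just have met stopping criteria that the lower doses did not. This stands as a further condition on the conflict.

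**The impact is small.** Dose selection is neither an objective nor an endpoint, the SAP lists no MTD table, and all safety data are shown by dose. This stands too. A careful reader could see how 5.0 and 10.0 μl/kg were tolerated.

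**The DEC Charter may hold the criteria.** It was not available. It may explain the DEC's recommendation, but Protocol 10.1 names the SAP as the place for the dose selection strategy.

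**Two stronger readings are tempting.** A reader might infer that the texts disagree whenever cohorts 1 and 2 both pass. That event includes every trial in which no cohort stops, and there 7.1 names no MTD to disagree with. For the same reason the documents do not support a four-fold disagreement (10.0 against 2.5 μl/kg) when no cohort stops. The 10.0 would be the reader's own value.

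**Conclusion.** The concern holds in a limited form. Protocol 10.6 brings efficacy into a quantity that the synopsis and 7.1 define by toxicity alone, and the SAP does not supply the rule that 10.1 assigns to it. The mismatch in wording is certain.

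Two different MTD values, 5.0 and 2.5 μl/kg, arise only if cohort 3 stops and the fallback both applies and is taken as the MTD. The first condition has probability 0.2% to 13.0% at flat assumed rates of 5% to 20%, and 2.6% to 61.4% under the three assumed rising profiles. Both ranges use full cohorts of 12 and a 4-of-12 trigger, with the SAE rule set aside. The width of the ranges shows that the assumed rates drive the answer. In two further outcomes, no stop and a cohort 1 stop, the defect is that 7.1 gives no MTD while 10.6 can be read as giving 2.5.

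The effect is confined to the reported dose conclusion. Escalation safety rests on 7.5.1.2 and the DEC and is not affected, nor are the descriptive summaries by dose. The point should be fixed, but it does not threaten the trial.

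**What to change.** 1. In Protocol 10.6, replace the MTD label with a recommended dose, capped at the MTD.
2. Keep the single safety-only MTD of the synopsis and 7.1, and complete it. If no cohort stops, report the MTD as not reached, at least 10.0 μl/kg. If cohort 1 stops, report none established, below 2.5 μl/kg, and therefore no recommended dose.
3. Put the recommended-dose rule in the SAP, including the lowest-dose fallback, with its endpoints and the sponsor's threshold for a clear benefit. Do this before database lock and before the central reads. The SAP itself says: "The SAP is finalized and signed prior to hard lock of the database".
4. State in the SAP that the rule may not be fully prospective for safety or for efficacy. Sponsor personnel sit on the DEC and may have seen cohort safety data. The study is open-label, early step-up depends on visible contrast effect (Protocol 7.1 and 7.5.1.2), and images go to the sponsor or contract research organization before reading (Protocol 16.1). The sponsor also supplies the suboptimal-echo classification (SAP 7.2.2). Writing the rule before the central reads therefore helps, but a reader should not infer that it guarantees a prospective efficacy rule.

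**Cost.** A short wording amendment, with ethics approval where Protocol 13.1 requires it, and one SAP paragraph. No new subjects, visits or data are needed. The downside is less room for judgement at the end of the study. An SAP paragraph alone would be cheaper, but it would leave the protocol using one term in two senses.
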